### **8.7. Safety Analysis**

Safety will be assessed via AEs, clinical laboratory tests, and concomitant medications. All safety data collected on or after the date that study drug was first administered up to the date of last dose of study drug plus 30 days will be summarized by cohort, indication and treatment in the Safety Analysis Set. Information regarding study drug administration, study drug compliance, and other safety variables will be summarized. Data for the pretreatment will be included in data listings.

### **8.7.1. Extent of Exposure**

A subject's extent of exposure to study drug data will be generated from the study drug administration data. Descriptive information will be provided by cohort, indication and treatment regarding the number of doses of study drug prescribed, the total number of doses taken, the duration of exposure to study drug, and the number and timing of prescribed dose interruptions.

GS-4224 compliance will be described in terms of the proportion of study drug actually taken based on returned pill count relative to the amount that was dispensed (taking into account physician-prescribed interruptions).

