**Treatment:**

Subjects who meet eligibility criteria will receive GS-4224 orally once daily in the 400 1500 mg QD cohorts and 1000 mg twice daily in the 1000 mg BID cohort (separated by approximately 12 hours). Each cycle will consist of 21 days. Safety and efficacy assessments will occur on an outpatient basis including assessment of tumor response, physical exam, vitals, ECG, collection of blood samples (for routine safety labs, GS-4224 PK, pharmacodynamic markers, and other biomarkers at applicable visits), urine pregnancy test (every 3 weeks while receiving GS-4224 in females of childbearing potential), and assessment of AEs. In addition, subjects will undergo postbaseline CT/MRI and PET-CT (for cHL) scans for tumor response assessment. A subject who does not show evidence of disease progression by clinical assessment or by CT/MRI or applicable scan may continue receiving study treatment until disease progression (clinical or radiographic), unacceptable toxicity, withdrawal of consent, or other reasons specified in Section 3.5.

After discontinuation of all study treatment, subjects will be followed for safety for 30 days.

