#### **5.2.2. Packaging and Labeling**

GS-4224 tablets are packaged in white, high density polyethylene bottles. Each bottle contains 30 tablets, silica gel desiccant, and polyester packing material. Each bottle is capped with a child-resistant polypropylene screw cap fitted with an induction sealed, aluminum-faced liner.

Study drug(s) to be distributed to centers in participating countries shall be labeled to meet applicable requirements of the FDA, European Union (EU) Guideline to Good Manufacturing Practice - Annex 13 (IMP), and/or other local regulations.

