### **5.2.3. Storage and Handling**

GS-4224 tablets should be stored refrigerated (2-8°C). Storage conditions are specified on the label. Keep bottles tightly closed to protect from moisture and allow them to warm to room temperature prior to opening. When a 100-mg bottle is removed from storage for dosing, keep tightly closed when not in use and store below 30°C for up to 4 weeks (28 days). The 200-mg and 500-mg tablets may be stored below 30°C for up to 12 weeks (84 days). Until dispensed to the subjects, all study drug bottles should be stored in a securely locked area, accessible only to authorized site personnel. To ensure the stability and proper identification, the drug products should be stored in the containers in which they were supplied.

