### **5.3. Dosage and Administration of GS-4224**

The GS-4224 study drug will be supplied as tablets in strengths of 100 mg, 200 mg, and/or 500 mg. GS-4224 will be taken once daily in the morning (400 1500 mg QD cohorts) and 1000 mg twice daily separated by approximately 12 hours (1000 mg BID cohort).

On days with intensive PK (Cycle 1 Days 1 and 15), study drug will be administered at the same time every morning with approximately 240 mL of water and following an overnight fast (no food or drinks, except water, for at least 8 hours). For study treatments including those of more than 5 tablets, up to an additional 120 mL of water can be administered, if necessary. Water will be withheld starting 1 hour before and for 2 hours after dose administration, except for water given with the study drug. Water may be consumed by subjects following the 2-hour blood draw for the remainder of the collection period. A meal (standardized lunch) will be provided to subjects after the 4 hour postdose blood draw. All other fluids will be allowed after the 4 hour postdose blood draw.

For all days that study drug is administered where no intensive PK assessments are required, GS-4224 should be administered without regard to food at approximately the same time every morning. Subjects should administer study drug with a full glass of water.

If vomiting occurs after administration of study drug, the dose should not be repeated.

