**Appendix 2. Study Procedures Table**

Study Phase Cycle Day	Screening Day -28 to Day 1	Cycle 1 (First 21 Days)						C2D1	C3D1	C4D1	C5D1	Every 3 weeks	Every 6 weeks	Every 9 weeks	EOT f	30 day Safety Follow-up f
		Cycle 1 Day 1	Day 2	Day 4	Day 8	Day 11	Day 15									
Window (day)	-28	±0	±0	±0	±1	±1	±2	±2	±2	±2	±2	±7	±7	±7	±7	±7
Informed Consent	X															
Medical and Medication History a	X															
Physical Examination b	X	X	X	X	X	X	X	X	X	X	X	X			X	
Vital Signs c	X	X	X	X	X	X	X	X	X	X	X	X			X	
12 lead ECG d	X	X			X		X	X	X	X	X	X d			X	X
Adverse events/ Concomitant medications e	X	X	X	X	X	X	X	X	X	X	X	X			X	X
Study Drug Dispensing		X						X	X	X	X	X				
Dosing Diary Accountability		X	X	X	X	X	X	X	X	X	X	X				
IXRS Registration	X	X						X	X	X	X	X			X	
CBC with differential	X g	X		X	X	X	X	X	X	X	X	X			X	
Coagulation	X g	X		X	X	X	X	X	X	X	X	X			X	
Chemistry	X g	X		X	X	X	X	X	X	X	X	X			X	
TSH		X											X			
Basal Cortisol		X											X			
Urinalysis		X			X			X	X	X	X	X			X	
Pregnancy Test h	X	X						X	X	X	X	X			X	

Study Phase Cycle Day	Screening Day -28 to Day 1	Cycle 1 (First 21 Days)						C2D1	C3D1	C4D1	C5D1	Every 3 weeks	Every 6 weeks	Every 9 weeks	EOT f	30 day Safety Follow-up f
		Cycle 1 Day 1	Day 2	Day 4	Day 8	Day 11	Day 15									
Window (day)	-28	±0	±0	±0	±1	±1	±2	±2	±2	±2	±2	±7	±7	±7	±7	±7
HIV/CD4+/HBV/HCV Testing i	X															
<h1 style="margin: 0;">CCI</h1>																
<h1 style="margin: 0;">CCI</h1>																
<h1 style="margin: 0;">CCI</h1>																
<h1 style="margin: 0;">CCI</h1>																
<h1 style="margin: 0;">CCI</h1>																
<h1 style="margin: 0;">CCI</h1>																
<h1 style="margin: 0;">CCI</h1>																
Tumor PD L1 IHC p	X															
Archival Tumor Tissue or pre treatment biopsy q	X															

Study Phase Cycle Day	Screening Day -28 to Day 1	Cycle 1 (First 21 Days)						C2D1	C3D1	C4D1	C5D1	Every 3 weeks	Every 6 weeks	Every 9 weeks	EOT f	30 day Safety Follow-up f
		Cycle 1 Day 1	Day 2	Day 4	Day 8	Day 11	Day 15									
Window (day)	-28	±0	±0	±0	±1	±1	±2	±2	±2	±2	±2	±7	±7	±7	±7	±7
CCI																
CCI																

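### Protocol 8.7.1 measures compliance against tablets dispensed, not prescribed, so surplus and leftover tablets count as non-compliance

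*Protocol*

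**What the plan says.** Protocol 8.7 commits to summarising study drug compliance as part of the safety analysis. Section 8.7.1 defines it as "the proportion of study drug actually taken based on returned pill count relative to the amount that was dispensed", with one adjustment: "taking into account physician-prescribed interruptions". The paragraph just before that sentence also plans descriptive summaries of doses prescribed, doses taken, duration of exposure and prescribed interruptions.

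The supply arrangements are spread over several sections:

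- Section 5.2.2: "Each bottle contains 30 tablets, silica gel desiccant, and polyester packing material", with a cap "fitted with an induction sealed, aluminum-faced liner".
- Section 5.2.3: "the drug products should be stored in the containers in which they were supplied". It also allows 200 mg and 500 mg tablets to be kept below 30°C for up to 84 days, and a 100 mg bottle for up to 28 days.
- Synopsis, Treatment: "Each cycle will consist of 21 days".
- Appendix 2, row "Study Drug Dispensing": Day 1 of Cycles 1 to 5, then every 3 weeks.
- Section 5.3: drug is "supplied as tablets in strengths of 100 mg, 200 mg, and/or 500 mg". No tablet mix per dose level is given.
- Section 5.6: used and unused drug goes back to the site. When it goes back, and whether leftovers are issued again, is not stated.

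The SAP does not carry the pill-count measure forward. SAP 4.2 reports total duration of exposure, and prescribed adherence within the 21-day DLT window (actual duration over protocol-specified duration). SAP 7.7 nevertheless declares that the safety analyses do not depart from the protocol.

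**The concern.** A compliance ratio should compare what was taken with what should have been taken. The amount dispensed is a different quantity, because it includes any planned surplus and whatever remains when treatment ends. Neither is a dose taken or a prescribed interruption, so the formula as written scores both as missed doses.

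Two things follow. The reported figure depends partly on how tablet strengths fill 30-tablet bottles, so the same behaviour can score differently under different mixes. It also falls when a subject stops partway through a supply, which ties apparent non-compliance to early discontinuation. At stake is the meaning of one descriptive summary. Section 8.7.1 holds the only whole-study compliance formula visible in either document.

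**Working it through.** The documents state no compliance figure, so there is nothing to reproduce. The check asks what the formula returns for a subject who takes every dose. I count tablets; Section 8.7.1 does not say whether tablets or mg are meant.

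**Inputs.** 30 tablets per bottle (5.2.2); 21 days per cycle (Synopsis); strengths of 100, 200 and 500 mg (5.3); dose levels 400, 700, 1000 and 1500 mg QD and 1000 mg BID (Table 3-1).

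**Case A: whole bottles each cycle, leftovers not reused (assumed).** With n tablets per day of a given strength, need = 21n and supply = 30 × ceil(21n/30). Compliance = sum of needs / sum of supplies over the strengths used.

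| Dose level | Fewest tablets per day | Result | 100 mg tablets only | Range over all mixes |
|---|---|---|---|---|
| 400 mg QD | 2×200 | 42/60 = 70% | 84/90 = 93.3% | 70% to 93.3% |
| 700 mg QD | 500+200 | 42/60 = 70% | 147/150 = 98% | 70% to 98% |
| 1000 mg QD | 2×500 | 42/60 = 70% | 210/210 = 100% | 70% to 100% |
| 1500 mg QD | 3×500 | 63/90 = 70% | 315/330 = 95.5% | 70% to 96.2% |
| 1000 mg BID | 4×500 | 84/90 = 93.3% | 420/420 = 100% | 77.8% to 100% |

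If supply also had to cover the ±7-day window on the three-weekly visits (a further assumption), 4 tablets per day would need 4 × 28 = 112 tablets, hence four bottles. A BID subject attending on schedule would then score 84/120 = 70%.

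**Case B: leftovers carried forward.** Cumulative taken over cumulative dispensed, for a single strength:

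- 2 tablets per day: 42/60 = 70%, 84/90 = 93.3%, 126/150 = 84%, 168/180 = 93.3%, 210/210 = 100% after Cycles 1 to 5.
- 3 tablets per day: 70%, 84%, 90%, 93.3%, 95.5% over the same cycles.
- 1 tablet per day (each strength in the 500+200 mix): 70% through Cycle 3, then 84/90 = 93.3% after Cycle 4.
- 4 tablets per day: 93.3% through Cycle 4, then 420/420 = 100% after Cycle 5.

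The first-cycle figure matches Case A. The later trend is upward but uneven.

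**Case C: stopping mid-supply.** This needs no whole-bottle assumption. Suppose exactly 42 tablets are dispensed for a cycle at 2 per day, and the subject stops permanently after day 7 with no missed dose. Taken = 14, returned = 28, compliance for that cycle = 14/42 = 33%. Permanent discontinuation is not a prescribed interruption, so the stated adjustment does not remove it.

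**With a prescribed denominator.** Cases A and B become 21n/21n = 100% per cycle at every dose level and mix. Case C becomes 14/14 = 100%.

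**The case against.** The strongest reply is that the formula may never be used. The visible SAP sections schedule no pill-count table, the SAP covers Phase 1b only for a synoptic report, and its adherence measure already has a protocol-specified denominator. Section 8.7.1 itself plans to summarise doses prescribed and doses taken, which are the components of a sound ratio. This stands, and it is why the point is minor. It does not dispose of the point: Protocol 8.7 still promises a compliance summary, and SAP 7.7 declares no departure from the protocol, so the formula has not been withdrawn.

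The second reply is that issuing fresh whole bottles every cycle is inferred. This also stands. The 84-day storage allowance equals four cycles, so the 200 mg and 500 mg tablets that give 70% in the fewest-tablet mixes could be carried forward. Case B then applies, and the shortfall shrinks with time on treatment.

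A reader might infer that compliant subjects will in fact be reported at 70%, or that four of the five dose levels fall below the plan's 75% mark. The documents do not support either. The tablet mix is not given, so 70% is a possible value and not the expected one. The 75% mark applies to prescribed doses (SAP 3.1.4, at least 16 of 21) and to duration-based adherence (SAP 4.2.2), never to tablets dispensed.

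**Conclusion.** The point holds as a minor defect in a descriptive definition. As written, the Section 8.7.1 denominator treats surplus tablets and tablets left at permanent discontinuation as non-compliance. Under whole-bottle dispensing without carry-over, full compliance scores 70% to 100% depending on tablet mix. With carry-over the cumulative figure rises towards 100%. The dispensing rule and the tablet mix are both assumptions; the discontinuation effect depends on neither.

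A reader might go further and infer that DLT evaluability, the MTD, or the reading of toxicity and efficacy by dose is compromised. The documents do not support that. DLT evaluability rests on prescribed doses, exposure is summarised by duration, SAP 3.5 plans no formal testing, and no visible analysis uses pill-count compliance as a criterion or covariate. Nor need the dose levels differ: under the fewest-tablet mix without carry-over, all four QD levels give the same 70%.

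**What to change.** Choose one of two.

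1. If whole-study compliance will be reported, change the denominator in Protocol 8.7.1 to the amount prescribed from first to last dose, excluding investigator-prescribed interruptions. Keep dispensed minus returned as the numerator, say whether the amounts are tablets or mg, and use this formula for every whole-study compliance table.
2. If pill-count compliance will not be reported, state in SAP 7.7 that it is replaced by the exposure and adherence measures of SAP 4.2. SAP Section 1 already provides for changes after finalisation to be documented in the CSR.

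Either costs a sentence. The first needs no new type of data: the numerator already relies on returned pill counts, and Section 8.7.1 already plans to summarise prescribed doses and the number and timing of prescribed interruptions. Section 5.6 describes accountability by kit, so the sponsor should confirm that tablet-level return counts reach the database; the present formula needs them too.

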### **8.7.2. Adverse Events**

AEs will be coded using the Medical Dictionary for Regulatory Activities (MedDRA). System Organ Class (SOC), High-Level Group Term, High-Level Term, Preferred Term (PT), and Lower-Level Term will be attached to the clinical database. The severity of AEs will be graded by the investigator according to the NCI-CTCAE, version 5.0, whenever possible. If a NCI-CTCAE criterion does not exist for a specific type of AE, the grade corresponding to the appropriate adjective will be used by the investigator to describe the intensity of the AE: Grade 1 (mild), Grade 2 (moderate), Grade 3 (severe), Grade 4 (life threatening), or Grade 5 (fatal). The relationship of the AE to the study drug will be categorized as related or unrelated.

All AEs will be listed. The focus of AE summarization will be on TEAEs. A TEAE is defined as any AE with onset date on or after the date of first dose of study drug up to 30 days after permanent study drug discontinuation or any AEs leading to premature study drug discontinuation. Summaries (number and percentage of subjects) of TEAEs by SOC and PT will be provided by cohort, indication, and treatment.

Summary tables will be presented to show the number and percentage of subjects reporting TEAEs by severity grade and corresponding percentages. A subject who reports multiple TEAEs within the same PT (or SOC) is counted only once for that PT (or SOC) using the worst severity grade. Separate listings and summaries will be prepared for the following types of TEAEs:

- Study drug-related AEs
- AEs that are Grade  $\geq 3$  in severity
- AEs leading to study drug interruption and/or dose modification
- AEs leading to study drug discontinuation
- SAEs

### 8.7.3. Laboratory Evaluations

Selected laboratory data will be summarized based on observed data. Data and change from baseline at all scheduled time points will be summarized. The focus of laboratory data summarization will be on treatment-emergent laboratory abnormalities. A treatment-emergent laboratory abnormality is defined as an abnormality that, compared to baseline, worsens by  $\geq 1$  grade in the period from the first dose of study drug to 30 days after the last dose of study treatment. If baseline data are missing, then any graded abnormality (ie, an abnormality that is Grade  $\geq 1$  in severity) will be considered treatment emergent.

Graded laboratory abnormalities will be defined using the NCI-CTCAE version 5.0 when applicable. Summary tables will be presented for each relevant assay to show the number of subjects by CTCAE severity grade with corresponding percentages. For parameters for which a CTCAE scale does not exist, the frequency of subjects with values below, within, and above the normal ranges will be summarized. Subjects will be characterized only once for a given assay, based on their worst severity grade observed during a period of interest (eg, during the study or from baseline to a particular visit).

Shift tables for selected laboratory data may also be presented by showing change in CTCAE severity grade from baseline to the worst grade after baseline. For parameters for which a CTCAE scale does not exist, shift tables presented will show change in results from baseline to the worst grade after baseline. Separate listings and summaries will be prepared for laboratory abnormalities that are Grade  $\geq 3$  in severity.

CCI

[Redacted]

CCI

[Redacted]

### 8.10. Sample Size

The sample size of the study will be determined based on the number of dose levels evaluated and the emerging GS-4224-related toxicities and efficacy. The study is planned to enroll approximately 120 subjects.

Approximately 44 subjects will be enrolled in the dose escalation phase (Phase 1b) CCI

Approximately 40 subjects will be enrolled into the Dose Expansion Cohort B1.

## **9. RESPONSIBILITIES**

### **9.1. Investigator Responsibilities**

#### **9.1.1. Good Clinical Practice**

The investigator will ensure that this study is conducted in accordance with International Council for Harmonisation (of Technical Requirements for Pharmaceuticals for Human Use) (ICH) E6(R2) GCPs and applicable laws and regulations.

#### **9.1.2. Financial Disclosure**

The investigator and subinvestigators will provide documentation of their financial interest or arrangements with Gilead, or proprietary interests in the investigational drug under study. This documentation must be provided prior to the investigator's (and any subinvestigator's) participation in the study. The investigator and subinvestigator agree to notify Gilead of any change in reportable interests during the study and for 1 year following completion of the study. Study completion is defined as the date when the last subject completes the protocol-defined activities.

#### **9.1.3. Institutional Review Board/Independent Ethics Committee Review and Approval**

The investigator (or sponsor as appropriate according to local regulations) will submit this protocol, ICF, and any accompanying material to be provided to the subject (such as advertisements, subject information sheets, or descriptions of the study used to obtain informed consent) to an IRB/IEC. The investigator will not begin any study subject activities until approval from the IRB/IEC has been documented and provided as a letter to the investigator.

Before implementation, the investigator will submit to and receive documented approval from the IRB/IEC any modifications made to the protocol or any accompanying material to be provided to the subject after initial IRB/IEC approval, with the exception of those necessary to reduce immediate risk to study subjects.

#### **9.1.4. Informed Consent**

The investigator is responsible for obtaining written informed consent from each individual participating in this study after adequate explanation of the aims, methods, objectives, and potential hazards of the study and before undertaking any study-related procedures. The investigator must use the most current IRB or IEC approved ICF for documenting written informed consent. Each ICF (or assent as applicable) will be appropriately signed and dated by the subject or the subject's legally authorized representative and the person conducting the consent discussion, and also by an impartial witness if required by local requirements. The ICF will inform subjects about pharmacogenomic testing and sample retention, and their right to receive clinically relevant pharmacogenomic analysis results.

### **9.1.5. Confidentiality**

The investigator must assure that subjects' anonymity will be strictly maintained and that their identities are protected from unauthorized parties. Only an identification code and any other unique identifier(s) as allowed by local law (such as year of birth) will be recorded on any form or biological sample submitted to the sponsor, IRB/IEC, or laboratory. Laboratory specimens must be labeled in such a way as to protect subject identity while allowing the results to be recorded to the proper subject. Refer to specific laboratory instructions. NOTE: The investigator must keep a screening log showing codes, names, and addresses for all subjects screened and for all subjects enrolled in the study. Subject data will be processed in accordance with all applicable regulations.

The investigator agrees that all information received from Gilead, including but not limited to the IB, this protocol, CRF/eCRF, the study drug, and any other study information, remain the sole and exclusive property of Gilead during the conduct of the study and thereafter. This information is not to be disclosed to any third party (except employees or agents directly involved in the conduct of the study or as required by law) without prior written consent from Gilead. The investigator further agrees to take all reasonable precautions to prevent the disclosure by any employee or agent of the study site to any third party or otherwise into the public domain.

### **9.1.6. Study Files and Retention of Records**

The investigator must maintain adequate and accurate records to enable the conduct of the study to be fully documented and the study data to be subsequently verified. These documents should be classified into at least the following 2 categories: (1) investigator's study file, and (2) subject clinical source documents.

The investigator's study file will contain the protocol/amendments; CRF and query forms; IRB/IEC and governmental approval with correspondence; ICF; drug records; staff curriculum vitae and authorization forms; and other appropriate documents and correspondence.

The required source data should include sequential notes containing at least the following information for each subject:

- Subject identification (name, date of birth, gender)
- Documentation that subject meets eligibility criteria, ie, history, physical examination, and confirmation of diagnosis (to support inclusion and exclusion criteria)
- Documentation of the reason(s) a consented subject is not enrolled
- Participation in study (including study number)
- Study discussed and date of informed consent
- Dates of all visits

- Documentation that protocol-specific procedures were performed
- Results of efficacy parameters, as required by the protocol
- Start and end date (including dose regimen) of study drug, including dates of dispensing and return
- Record of all AEs and other safety parameters (start and end date, and including causality and severity)
- Concomitant medication (including start and end date, dose if relevant; dose changes)
- Date of study completion and reason for early discontinuation, if it occurs

All clinical study documents must be retained by the investigator until at least 2 years or according to local laws, whichever is longer, after the last approval of a marketing application in an ICH region (ie, US, Europe, or Japan) and until there are no pending or planned marketing applications in an ICH region; or, if no application is filed or if the application is not approved for such indication, until 2 years after the investigation is discontinued and regulatory authorities have been notified. Investigators may be required to retain documents longer if specified by regulatory requirements, by local regulations, or by an agreement with Gilead. The investigator must notify Gilead before destroying any clinical study records.

Should the investigator wish to assign the study records to another party or move them to another location, Gilead must be notified in advance.

If the investigator cannot provide for this archiving requirement at the study site for any or all of the documents, special arrangements must be made between the investigator and Gilead to store these records securely away from the site so that they can be returned sealed to the investigator in case of an inspection. When source documents are required for the continued care of the subject, appropriate copies should be made for storage away from the site.

